
Aim 1: Demonstrate the feasibility of use of PENFS to treat PSH, and tolerability of the device. Hypothesis: The PENFS device will be well tolerated, defined as < 10% early termination from the study. We will recruit 20 patients with ASBI and PSH who will receive PENFS therapy.
 
Aim 2a: Evaluate the feasibility of capturing pediatric PSH symptoms using the CFS scoring tool. Hypothesis: It is feasible to monitor the severity of PSH using a CFS scoring tool (Table 1a,1b). The scoring tool will be adapted for the appropriate age range of the patient (Table 2). We aim for at least 80% scoring (<math>\geq 8/10</math> scheduled scoring per protocol while the device is worn).
 
Aim 2b: Evaluate the effectiveness of the PENFS device in reducing PSH symptoms using change in CFS score. Hypothesis: A decrease in CFS severity score with use of PENFS will be associated with a lower number and/or doses of maintenance and rescue medications for control of PSH symptoms.
 
Aim 3a: Evaluate the change in autonomic balance with use of PENFS device Hypothesis: Heart Rate Variability (HRV) and pupillometry parameters that correspond to sympathetic and parasympathetic activity will be different after PENFS device placement compared to before, reflecting an increase in parasympathetic tone. All patients will be on routine continuous EKG monitoring in the PICU during the study period of interest. Similarly, pupillometry is routinely performed in patients with ASBI in the PICU.
 
Aim 3b: Evaluate feasibility of measuring PENFS effectiveness in treating PSH by a decrease in medication use. Hypothesis: It would be feasible to use the maintenance and rescue medication dosing and frequency as a marker of severity of PSH. PENFS device use will result in lesser number and/or doses of maintenance and rescue medications for control of PSH symptoms. We will compare the pilot sample to a historical cohort to allow power analysis and sample size calculation for a future larger efficacy trial, recognizing that this pilot study is not powered for efficacy.

D. Background, significance, and rationale (including description of preliminary studies and any results):

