### **Aim 3b: Evaluate feasibility of measuring PENFS effectiveness in treating PSH by a decrease in medication use**

**Methods:** The maintenance medications and the number of doses and type of rescue medications administered will be collected for every 24 hours (0-24h, 25-48h, 49-72h, 73-96h, 97-120h, 121-144h, 145-168h, 169- 192h) for the enrolled patients. These will be compared to a historical cohort of PSH patients. The historical cohort will consist of PSH patients (2-17 years old) identified using the ICU Neurology administrative dataset from January 2018 – August 2021. This dataset will be used to identify ASBI patients who likely developed PSH. Eligible patients with PSH will be identified and relevant data collected by individual chart review. During this period all the PSH patients were followed by ICU Neurology thus ensuring a uniform approach to their treatment. We have also developed a practice guideline for treatment of PSH that will ensure uniform treatment of these patients during the study period. Similar to Aim 2a, we will examine the need for additional maintenance medications or change in frequency of rescue medications with discontinuation of the device. We hypothesize that, with discontinuation of the device, the patients may experience worse PSH symptoms as demonstrated by increasing CFS score and need for additional maintenance and/or rescue medications.

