## Protocol Summary/Submission Application

*Hypothesis 1:* The number approached and consented will be tracked. Reactions/ adverse events will be summarized and reasons for early termination, if any, evaluated.

*Hypothesis 2a, 2b:* The scoring tool will be adapted for the appropriate age range of the patient (Table 2). We aim for at least 80% scoring ( $\geq 8/10$  scheduled scoring per protocol while the device is worn). The association of the score and the number of doses of maintenance and rescue medications will be summarized with a spearman correlation and exact 95% Confidence intervals (CI).

*Hypothesis 3a:* HRV and Pupillometry measures will be tracked over time with any loss of data recorded with reasons. Wilcoxon Rank Sum test will be used to compare the mean  $\pm$ SD for the parameters for the 12-hour periods before and after device placement.

*Hypothesis 3b:* The number of doses of maintenance and rescue medications for control of PSH symptoms will be compared to historic data using a t-test or non-parametric Mann Whitney. Further a classification tree will be used to evaluate the effect of demographics, clinical history and use of PENFS.

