**D. Describe procedures to be employed in analyzing data (including a power analysis):**

*This is a pilot feasibility study of use of the device. A convenience sample of 20 patients was chosen.*

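### Hypothesis 3b gives no covariate-adjusted PENFS effect and no confidence interval; its only multivariable step against the historical cohort is a classification tree

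*Combined protocol and SAP*

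**What the plan says.** In the combined protocol and SAP, the analysis text for Hypothesis 3b names the outcome and comparator: "The number of doses of maintenance and rescue medications for control of PSH symptoms will be compared to historic data". For the test it offers a choice between a parametric and a rank method: "using a t-test or non-parametric Mann Whitney". The next sentence adds the tree: "Further a classification tree will be used to evaluate the effect of demographics, clinical history and use of PENFS". The tree's response variable, its splitting, pruning and validation rules, and any class boundaries are not stated.

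The comparator is a set of earlier PSH patients "identified using the ICU Neurology administrative dataset from January 2018 – August 2021" (Aim 3b, Methods) and confirmed by chart review. Its size is not given. The treated group is small: "A convenience sample of 20 patients was chosen" (Section 6, item D).

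The purpose is set out under Aim 3b in the specific aims: "We will compare the pilot sample to a historical cohort to allow power analysis and sample size calculation for a future larger efficacy trial". The same sentence ends with a disclaimer about what the sample can show: "recognizing that this pilot study is not powered for efficacy".

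The data analysis overview lists the CART family, which includes regression trees, among exploratory tools. It reserves mixed models for changes over time in continuous data. The only confidence interval in the hypothesis-by-hypothesis plan is for the Spearman correlation under Hypotheses 2a and 2b.

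**The concern.** Treated and historical children were not randomised, and the overview's own design justification describes these patients as heterogeneous. A comparison of dose counts therefore needs some allowance for case mix. The two-sample test makes none. The tree is the only step that considers PENFS together with other variables, and the plan gives it the job of assessing the device's effect.

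A tree does not do that job. It returns a sequence of splits and a summary within each leaf. If PENFS is never chosen as a split, there is no PENFS result at all. If it is chosen low in the tree, the contrast applies only to the subgroup above that split. In neither case is there one adjusted difference with a measure of uncertainty.

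What is at stake is the planning use of Aim 3b. A later sample size calculation needs a plausible effect and an idea of how uncertain it is. As written, the plan would hand over an unadjusted p-value and a tree diagram.

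**Working it through.** **1. The plan's own figure.** The only number behind the treated group is recruitment arithmetic. From the stated 35 to 40 PSH patients and 60% enrolment: 35 × 0.60 = 21 and 40 × 0.60 = 24. From the raw inputs: 380 × 0.08 × 0.60 = 18.2 and 400 × 0.10 × 0.60 = 24.0. The stated 20 lies in that wider range. No effect size, standard deviation, alpha or power is given for Hypothesis 3b, so there is no power calculation to reproduce.

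**2. What each planned analysis delivers for PENFS versus historical**

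| Analysis | Adjusted for case mix | Effect estimate with interval |
|---|---|---|
| t-test or Mann-Whitney | No | None named |
| Classification tree | Considers covariates | None |
| Mixed models (overview) | Not tied to this comparison | Not applicable |

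**3. How informative is a split on PENFS?** The documents give no dose distribution or historical size, so every input here is an assumption: 20 treated; 20, 40 or 120 historical; reference mean 15 doses; negative binomial counts with dispersion 0.5; five covariates; no confounding; unpruned trees of depth 3 with at least 5 children per leaf; 400 runs per setting. The classification tree used counts split at the median, and the regression tree used raw counts. The table shows how often PENFS appeared anywhere in the tree.

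| Historical n | Class. tree, RR 0.7 | Class. tree, RR 1.0 | Regr. tree, RR 0.7 | Regr. tree, RR 1.0 |
|---|---|---|---|---|
| 20 | 38% | 26% | 48% | 28% |
| 40 | 42% | 24% | 50% | 28% |
| 120 | 38% | 17% | 41% | 17% |

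For the classification tree, seeing PENFS is only 0.38/0.26 = 1.5, 0.42/0.24 = 1.8 and 0.38/0.17 = 2.2 times as likely under a real 30% reduction as under none. For the regression tree the ratios are 0.48/0.28 = 1.7, 0.50/0.28 = 1.8 and 0.41/0.17 = 2.4. With a real 30% reduction, PENFS was the first split in only 10%, 12% and 6% of classification trees. Simulation error is about √(0.4 × 0.6/400) = 0.024, or 2.4 percentage points.

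**4. What a count model gives on the same data.** A negative binomial regression with PENFS and the five covariates gave a rate ratio and 95% interval in every run, with coverage of 93% to 95%. At a true rate ratio of 0.7 the median interval was the estimate divided and multiplied by 1.63, 1.51 and 1.44 for 20, 40 and 120 historical children. For an estimate of 0.7 that means:

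- 20 historical: 0.7/1.63 = 0.43 to 0.7 × 1.63 = 1.14
- 40 historical: 0.7/1.51 = 0.46 to 0.7 × 1.51 = 1.06
- 120 historical: 0.7/1.44 = 0.49 to 0.7 × 1.44 = 1.01

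The intervals are wide, but they state the uncertainty that planning needs. The coverage is a best case: the model was given the true dispersion and the data were generated from the same family.

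**5. Which covariates can be used.** The data collection section lists demographics and cause of brain injury for both groups, so age and cause are available. Historical medications are collected only from the time the CFS exceeds 6. Table 3 gives enrolled children a 12-hour pre-device medication window, but nothing matching it is planned for the historical group. A pre-index dose rate therefore cannot be a covariate.

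**6. Time zero.** Treated children are counted from device placement, which may be up to 24 hours after the CFS criterion is met. Historical children are counted from the criterion itself. No regression on the collected data removes that offset.

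**The case against.** The strongest reply is that this is a feasibility pilot on a convenience sample, that the aims disclaim power for efficacy, that the overview puts CART among exploratory methods, and that the tree follows the main comparison as an extra. Means and variances for a later sample size can be taken from the raw data, a t-test can be accompanied by an interval even though none is named, and historical-control confounding would survive any model.

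Much of that stands, and it limits the weight of the point. It does not close the gap. The Hypothesis 3b text gives the tree the specific task of assessing the device's effect. Raw means and an unadjusted interval still leave the planning difference open to case mix. Lack of power is a reason to report an estimate with its interval, not a reason to omit one.

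A reader might go further and infer that dose counts must be cut into classes, with a calculable loss of information. The documents do not support that. The tree's response is not stated, no cut-point is given, and the overview's wording leaves room for a regression tree, which takes counts directly.

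A reader might also infer that the tree is grown on 20 children and can make only a couple of splits. PENFS can be a predictor only if treated and historical children are pooled, so the total exceeds 20. As an assumption, 44 months at 35 to 40 PSH patients a year gives 44/12 × 35 = 128 to 44/12 × 40 = 147 candidates before chart review.

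**Conclusion.** The point holds as a moderate one. Hypothesis 3b plans no covariate-adjusted PENFS effect and no interval, although the aims want the comparison to inform the next trial. That conclusion rests on the text alone and is the same for a classification or a regression tree.

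The size is illustrative. Under the assumed inputs, PENFS appears in 38% to 42% of classification trees when a 30% reduction is real and in 17% to 26% when there is none, so its presence or absence is weak evidence either way. A stated pruning rule or a different dose distribution would change these percentages.

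The point does not show that the pilot's feasibility aims fail, and an adjusted model would not turn the historical comparison into evidence of efficacy.

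**What to change.** In the Hypothesis 3b analysis text:

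- Make the adjusted analysis a count model, negative binomial or quasi-Poisson, with robust standard errors and log observation time as offset. Include terms for PENFS, age and cause of ASBI.
- Fit it separately to rescue doses and to maintenance doses over the 120-hour window, because the hypothesis covers both. Report each rate ratio with its 95% confidence interval.
- Keep Mann-Whitney as the unadjusted check.
- Label the tree exploratory, in line with the overview, and state its response variable.
- Do not include a pre-index dose rate unless the historical chart review is extended to collect one.
- State two limitations: time zero differs between the groups by up to 24 hours, and residual confounding by the historical control remains.

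The cost is analysis wording, with no added patients or procedures. The historical abstraction must record dose counts for both drug classes, which the hypothesis already presupposes. The downside is a parametric model with few covariates in a small sample; the rank test gives a check on the unadjusted comparison.

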## Protocol Summary/Submission Application

**F. Research procedures such as lab draws (including volume of samples), ECG, imaging, clinical procedures, genetic testing, surveys (may attach activity table if available):**

**Describe what will happen to the subject solely for the purpose of this research study:**

- 1) Placement of PENFS device on the external ear of the enrolled patient by study investigator or one of trained P-TRU nurses (RNs) that will remain in place for 120 hours.
- 2) CFS scoring per protocol by the bedside nurse
- 3) Evaluation of heart rate variability using EKG data obtained from the bedside monitor during the 12 hour period before and after placement of PENFS device.
- 4) *The bedside RN, TRU RN, or physician will remove the device and dispose of properly in a sharps container. The devices are easily removed by removing the tape and adhesives.*
- 5) Parental survey of their perceptions about the use of the device at the end of the study.

**Describe what is happening per protocol but is considered part of routine care (would happen even if the individual did not participate):**

- 1) Pupillometry
- 2) Medical management of PSH

### Clinical Trial

**A. Is this study a Clinical Trial/Clinical Investigation?**

**Clinical Trial** means a research study in which one or more human subjects are prospectively assigned to one or more interventions (which may include placebo or other control) to evaluate the effects of the interventions on biomedical or behavioral health-related outcomes. [45 CFR 46.102(b)]

**Clinical Investigation** means any experiment that involves a test article and one or more human subjects, and that either must meet the requirements for prior submission to the Food and Drug Administration under section 505(i) or 520(g) of the act, or need not meet the requirements for prior submission to the Food and Drug Administration under these sections of the act, but the results of which are intended to be later submitted to, or held for inspection by, the Food and Drug Administration as part of an application for a research or marketing permit. The term does not include experiments that must meet the provisions of part 58, regarding nonclinical laboratory studies. The terms research, clinical research, clinical study, study, and clinical investigation are deemed to be synonymous for purposes of this part. [21 CFR 56.102(c)]. Note: this also include biospecimens.

No If NO, skip questions B-H  Yes If YES, answer the following questions B-H:

**B. What [phase of clinical trial](#) best describes this research?**

Phase I  Phase I/II  Phase II  Phase II/III  Phase III  Phase IV  
 Feasibility  Pivotal ([Feasibility vs Pivotal device studies](#))

**C. Is this trial "first-in-human" (in clinical trials, the first Phase-1 study in which a test product is administered to human beings)?**

No  Yes

If YES, the protocol must contain an adequate description of the pre-clinical research and/or other relevant data that supports the performance of the study.

## Protocol Summary/Submission Application

**D. Is this trial the first in a population (e.g., children)?** No  Yes

If YES, the protocol must contain an adequate description of the pre-clinical research and/or other relevant data that supports the performance of the study in the new population.

**E. Does this trial evaluate one or more [FDA-regulated products](#)?**

*Human Cells, Tissues, and Cellular and Tissue-Based Products (HCT/P's) may be classified as drugs, devices, and/or biologics. Information on the classification of HCT/P's is available on this [FDA website](#).*

*The 21st Century Cures Act excludes certain medical and decision support software from the definition of medical device meaning that such software is not subject to FDA regulations. Information regarding these exclusions is available on FDA's website for [digital health](#). If uncertain whether a product under investigation is a medical device, contact the CW HRPP office.*

 No  Yes If YES, indicate the following:

**Product Type(s):** Percutaneous electrical nerve field stimulator

**Product Name(s):** IB Stim

If YES, also include in the submission package **IRB – Supplement Form – Drugs and Biologics** for studies of drugs and biologics and/or **IRB – Supplement Form – Devices** for medical device studies. These forms are found in IRBNet under Forms and Templates.

**F. Will this trial enroll pregnant women or minors/women who are of child-bearing potential?** No  Yes

If YES, the protocol and consent must contain an adequate description of any known or anticipatable risks to pregnant women and fetuses and any measures to mitigate those risks. Birth control requirements, if applicable, must also be described. CW template pregnancy test language regarding disclosure of results must be included in parental permission/assent documents.

**G. Does the sponsor intend to collect data on “pregnant partners” (sexual partners of clinical trial subjects who become pregnant while the subject is receiving investigational agents)?** No  Yes

If YES, review Children's Wisconsin IRB [Position Statement Pregnant Subjects and Pregnant Partners](#) found in IRBNet under Forms and Templates and on the HRPP web pages.

## Protocol Summary/Submission Application

**H. Is this trial registered in [ClinicalTrials.gov](https://clinicaltrials.gov)?**

Contact MCW CTSI if there are questions about what needs to be registered or visit their [website](#) for registration instructions.

**N/A, registration is not required for this trial (confirm with CTSI if uncertain)**

**No, but trial will be registered prior to enrolling any subjects**

**Yes, ClinicalTrials.gov #: NCT05343988**

**For FDA-regulated and NIH funded clinical trials that are or will be registered in ClinicalTrials.gov, the following statement must be included verbatim in the consent/parental permission forms:**

**FDA:** "A description of this clinical trial will be available on <http://www.ClinicalTrials.gov>, as required by U.S. Law. This Web site will not include information that can identify you. At most, the Web site will include a summary of the results. You can search this Web site at any time."

**NIH:** "A description of this clinical trial will be available on <http://www.ClinicalTrials.gov>. This Web site will not include information that can identify you. At most, the Web site will include a summary of the results. You can search this Web site at any time."

### Risks

**A. Describe potential research-related risks and discomforts (consider physical, psychological, legal, social/economic/financial, loss of confidentiality, group harms); describe the probability, magnitude, and duration of the potential risks; do not address risks that would be present if the individual did not participate:**

Local discomfort/pain, skin irritation. Theoretical risks include cardiac dysrhythmia and new-onset seizures neither of which have been reported in previous studies. In a randomized sham-controlled trial of the use of the device for 115 children with functional abdominal pain, only 1 patient among 60 with active device discontinued treatment due to discomfort, whereas 6 patients in the sham-group discontinued the device one being adhesive allergy. Patients will be monitored (including EKG monitoring at least in the initial 48 hours of the device) as inpatient during the time the device is in place. Other studies have also reported minimal to no side-effects using the device for other indications.

Other risks include remote possibility of loss of confidentiality if there is any breach of study data.

**B. Describe steps taken to minimize risks:**

Patient comfort will be monitored to assess tolerability, skin will be monitored for contact dermatitis. EKG/Heart rate monitoring for dysrhythmia and monitoring for new onset clinical seizures. To minimize the remote possibility of a breach in confidentiality, patient data including PHI will be assigned a study ID and stored in a password-protected Excel file on MCW's secured drive: and be only accessible to limited members of the study team. Only coded data with a Study ID will be entered into the password-protected REDCap database.

### Section 2 Regulatory Criterion for Approval: Benefits

**Risks to subjects are reasonable in relation to anticipated benefits, if any, to subjects, and the importance of the knowledge that may reasonably be expected to result. In evaluating risks and benefits, the IRB should consider only those risks and benefits that may result from the research (as distinguished from risks and benefits of therapies subjects would receive even if not participating in the research).**

➤ If there is no benefit and no knowledge to be gained, there is no justification to expose subjects to risk.

**Protocol Summary/Submission Application****A. Describe the potential benefits to science and/or society which may accrue as a result of this research:**

If found to be effective in treatment of PSH, the PENFS device will offer a non-medication modality for treatment of PSH thus helping to decrease the need for neurosedative medications and decreasing the adverse effects of the medications.

The natural history of PSH is that the symptoms are worse initially requiring multiple medications to ameliorate the symptoms. Over time, the PSH symptoms decrease allowing weaning of some of the medications. Thus, the PENFS device might offer significant benefit in the initial period helping to limit the number of medications needed to control the symptoms of PSH.

**B. Are there any benefits which may accrue to the individual subjects in this research (compensation is not considered a benefit)?**

No  Yes

If YES, describe: Improvement in PSH symptoms and reduction in need for medications to treat PSH could potentially decrease the adverse effects associated with use of these medications.

